5.3.3 Study treatment discontinuation

A subject is considered to have prematurely discontinued double-blind study treatment if the 'reason for treatment end' in the **Study drug Log** eCRF is 'PREMATURE DISCONTINUATION' and the 'Study Period' is 'DB TREATMENT'. The reason for premature discontinuation will be taken from the **Premature Discontinuation of Study Treatment** eCRF and the study period is 'DB TREATMENT'.

Discontinuation from run-in study treatment is defined similarly and the reason will be taken from the same eCRF, but with study period = 'RUN-IN TREATMENT'. Discontinuation from withdrawal study treatment (listed only) is defined similarly with study period = 'SB WITHDRAWAL'. In those cases where a subject completed the double-blind treatment period, but did not start the withdrawal period, the reason for treatment discontinuation will be allocated to the withdrawal period.

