3.2 Study design rationale

This study is designed to select doses to be investigated in the Phase 3 program. The design of this dose-finding study meets the requirements laid out by international guidelines [ICH 2000a, ICH 2000b, EMA 2010] and literature [Rose 1990, Myers 2001].

In accordance with the regulatory guidelines, the study has a placebo run-in period of 4 to 6 weeks. The administration of placebo during this period minimizes bias due to the regression-toward-the-mean phenomenon [EMA 2010]. The placebo run-in period is 4 weeks for anti-hypertensive treatment-naïve subjects at Visit 1. For subjects receiving anti-hypertensive treatment at Visit 1, a 2-week placebo wash-out period is added to the 4-week run-in period. For these subjects the SB placebo run-in period is 6 weeks.

A 2-week SB placebo withdrawal period is introduced at the end of the study to investigate the withdrawal phenomena, i.e., rebound effect on BP.

^{**} Only for women of childbearing potential.

DB = double-blind; EOS = End-of-Study; EOT = End-of-Treatment; FU = follow-up, SB = single-blind, WD = withdrawal.

Essential hypertension Protocol AC-080A201 Version 3 30 May 2016, page 38/112

Confidential

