2 STUDY DESIGN AND FLOW

2.1 Study design

Study AC-080A201 is a prospective, multi-center, double-blind, double-dummy, randomized, placebo- and active-reference, parallel group, Phase 2 dose-finding study with ACT-132577 in subjects with essential hypertension (grade 1 and 2).

Approximately 1000 subjects are enrolled into the study, in order to have at least 540 subjects randomized in the 6 following groups using a 1:1:1:1:1:1 ratio: placebo, 5 mg ACT-132577, 10 mg ACT-132577, 25 mg ACT-132577, 50 mg ACT-132577 and lisinopril 20 mg. At least 420 subjects are expected to complete the trial. There are no stratification factors.

The study consists of the following study periods:

Screening

The screening period starts with the signature of the “study” informed consent form and lasts until Visit 1. During this period study assessments (e.g., laboratory test) are performed to determine whether the subject is eligible for the study.

Run-in period (Period I)

Period I is a single-blind (SB) placebo period of 4 to 6 weeks starting at Visit 1 and ends at Visit 4 / Randomization (after completion of the baseline 24-hour ambulatory blood pressure monitoring [ABPM] recording on the last dose of SB study treatment [placebo]).

The run-in period lasts 4 weeks for anti-hypertensive treatment naïve subjects.

The run-in period lasts 6 weeks for subjects on anti-hypertensive treatment including a 2-week wash-out period for anti-hypertensive treatment. The anti-hypertensive treatment must be discontinued (according to its label) at Visit 1, if there is no contraindication to stop it.

Treatment period (Period II)

Period II is a double-blind (DB) treatment period of 8 weeks which starts at Visit 4 with the first dose of DB study treatment and ends at Visit 7 at the first dose of SB withdrawal treatment.

Withdrawal period (Period III)

Period III is a SB placebo period of 2 weeks, which starts at Visit 7 with the first administration of first placebo dose (withdrawal [WD] study treatment) and ends at Visit 8 (WD-End-of-Treatment [EOT]).

Follow-up period

The follow-up period, including follow-up telephone call, or follow-up visit only for women of childbearing potential to perform the pregnancy test at the site, starts after the last dose of SB WD study treatment (placebo) and ends at 30–33 days after the last dose of the DB treatment.

End-of-Study (EOS)

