5.6.4 Adverse events leading to discontinuation of study treatment

These are AEs with ‘Action taken with study drug’ recorded as ‘permanently discontinued’ on the **Adverse Event** eCRF.

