10.5.3 Study treatment discontinuation

A summary table is provided for the SAF to display counts and percentages of subjects who prematurely discontinued double-blind study treatment, as well as the associated reasons [see definition in Section 5.3.3], by treatment group and overall.

Note that premature double-blind study treatment discontinuation does not necessarily imply study withdrawal.

In addition, premature run-in treatment discontinuation will be summarized for the RIS.

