11.7 Withdrawal period start date/time

The withdrawal period start date is the first day of intake of placebo during the withdrawal period. It is derived from the first treatment start date (in chronological order) in the **Study Drug Log** eCRF where the ‘Study Period’ is ‘SB WITHDRAWAL’. If the time of the WD period is missing the time of last assessment of ABPM at Visit 7 will be used, otherwise it will be set to 23:59.

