13.4.3 Study treatment discontinuation

Output name	Display*	Title (Description)	Analysis set(s)	Key	Mock layout
PDISCTR	T	Reasons for premature discontinuation of double-blind study treatment	SAF	Yes	LAYDISP003b
PDISCTR	T	Reasons for premature discontinuation of run-in treatment	RIS		LAYDISP003b
PDISCTR	L	Listing of subjects who discontinued treatment	RIS		LSTCSR012

* T = Summary Table; L = Listing.

RIS = Run-in Set; SAF = Safety Set.

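### AEs that stop the withdrawal placebo are mixed by dose arm into the double-blind AE-discontinuation tables, and non-AE reasons for not starting or stopping that placebo are not tabulated by arm

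*SAP*

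**What the plan says.** On AEs leading to discontinuation, SAP 5.6.4 gives a single condition: "These are AEs with ‘Action taken with study drug’ recorded as ‘permanently discontinued". It does not ask which period's treatment was stopped. SAP 5.6.1.1 counts an AE as double-blind treatment-emergent if its onset is between double-blind start and double-blind end plus 30 days. SAP 13.9.4 then tabulates such AEs on the Safety Set, by system organ class and preferred term (TEAEPDSCPR, marked Key) and by preferred term alone (TEAEPDPR). There is a run-in version of TEAEPDPR but no withdrawal-period table.

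On treatment stops, SAP 5.3.3 does use the period: a premature double-blind stop requires the Study Drug Log period to be DB TREATMENT. SAP 10.5.3 tabulates "counts and percentages of subjects who prematurely discontinued double-blind study treatment, as well as the associated reasons". In SAP 13.4.3 this is PDISCTR ("Reasons for premature discontinuation of double-blind study treatment"), also marked Key, with a run-in counterpart only. For the withdrawal period, SAP 5.3.3 says "Discontinuation from withdrawal study treatment (listed only) is defined similarly". It adds that for a subject who finished double-blind treatment but "did not start the withdrawal period, the reason for treatment discontinuation will be allocated to the withdrawal period".

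The SAP dates that period from dosing. Period II "ends at Visit 7 at the first dose of SB withdrawal treatment" (SAP 2.1), and "The withdrawal period start date is the first day of intake of placebo during the withdrawal period" (SAP 11.7).

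Protocol 3.2 gives the purpose of the withdrawal period: "to investigate the withdrawal phenomena, i.e., rebound effect on BP". Protocol 11.3.5 commits to repeating all safety analyses in the subjects who took part in the withdrawal period, using that period's data. SAP 4.1.3, which lists changes to the safety analyses, does not mention dropping this.

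**The concern.** The trial selects Phase 3 doses on the balance of efficacy and tolerability (Protocol 1.3), and AEs leading to premature discontinuation are a named safety endpoint. Two Key tables bear on this, and they follow different rules. The disposition table filters on the period of the treatment stopped; the AE table does not. A subject who takes the full eight weeks of a dose and then stops the placebo because of an AE is a double-blind completer in the first table and an AE discontinuation for that dose in the second. A reader comparing doses cannot tell from the AE table which treatment was stopped.

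The second gap concerns double-blind completers. If such a subject never starts the withdrawal placebo, or starts and stops it, the reason is found only in a listing. Where the reason is not an AE, for example blood pressure confirmed above the limit in Protocol 5.1.12, which applies throughout the study, no by-arm table of treatment-stop reasons shows it. The subject who never starts is also assigned to a period that, by SAP 2.1 and 11.7, has no start date for that person.

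**Working it through.** The plan gives no figure to reproduce. The check follows the rules through to the tables, then tests by day arithmetic whether withdrawal dosing lies inside the window.

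**1. Is withdrawal dosing inside the double-blind treatment-emergent window?**

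Inputs:
- Last double-blind dose: Visit 7 / Part 1, Day 55 ± 5 (Protocol 8.2.4.1).
- First withdrawal placebo dose: the next morning, Visit 7 / Part 2 (Protocol 5.1.4.3 and 8.3.1).
- Last withdrawal placebo dose: the day before Visit 8 (Protocol 5.1.4.3).
- Visit 8: Day 70 ± 3 (Protocol 8.3.2).
- Window: double-blind end + 30 days (SAP 5.6.1.1).

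Formula: last placebo day relative to double-blind end = (Visit 8 day − 1) − Visit 7 day.
- Nominal: (70 − 1) − 55 = +14; Visit 8 at 70 − 55 = +15.
- Latest case (Visit 7 on Day 50, Visit 8 on Day 73): (73 − 1) − 50 = +22; Visit 8 at +23.
- Earliest case (Visit 7 on Day 60, Visit 8 on Day 67): (67 − 1) − 60 = +6; Visit 8 at +7.

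All are below +30. Every AE with onset during on-schedule withdrawal dosing is therefore double-blind treatment-emergent.

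This rests on a reading. SAP 5.6.1.1 points to Sections 11.2 and 11.4 for double-blind start and end, but those sections now define run-in start and randomization. The definitions named in the text are in 11.5 and 11.6, which I used. Taken literally, the window would close at randomization + 30 days, i.e. Day 1 + 30 = Day 31, before the withdrawal period begins, and the AE part of this point would not arise.

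**2. Following one subject through the tables**

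Take a subject who completes double-blind treatment, starts withdrawal placebo and stops it for a new AE.
- PDISCTR: not counted, because the stop is not in period DB TREATMENT.
- TEAEPDSCPR and TEAEPDPR: counted under the dose arm, because the action is permanent discontinuation and the onset is within +30 days.
- The AE listing gives the period of onset (SAP 10.9.1). That is not the period of the drug stopped: an AE can begin on double-blind drug and lead to a stop of the placebo.

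Now take a double-blind completer who does not start, or stops, the placebo for confirmed high blood pressure with no AE recorded as the cause.
- PDISCTR: not counted.
- AE tables: not counted.
- Study-discontinuation table (PDISCST, SAP 13.5): counted only if the subject also leaves the study, and then under death, loss to follow-up, or a subject, physician or sponsor decision (SAP 5.4), none of which names blood pressure. Protocol 5.1.11 says a premature treatment stop is not in itself study withdrawal.
- What remains is a listing.

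**3. Weight of one subject**

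SAP 4.2 gives 490 randomized. Assuming six equal arms, all treated: 490/6 = 81.7, about 82 per arm. One subject is 100/81.7 = 1.22 percentage points; an assumed three in one arm would be 300/81.7 = 3.67 points. At the original 90 per arm, one subject is 1.11 points. The documents give no count of affected subjects.

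**The case against.** The best defence is that the plan is consistent in what it calls things. The protocol endpoint and the AE tables refer to study treatment, and the withdrawal placebo is also called study treatment. Charging AEs within 30 days to the randomized arm is a common safety convention, and it has pharmacological support here: with a half-life of about 44 hours (Protocol 1.2.1), five half-lives are 220 hours, or about 9 of the 14 withdrawal days. An AE in that time may be carry-over or rebound, so removing it from the per-dose display would lose information. This stands, and it is why the tables should be split rather than filtered. It does not answer the lack of separation within a table headed double-blind.

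A reader might infer three stronger things that the documents do not support.
- That stops are booked to the wrong period. The allocation rule in SAP 5.3.3 covers only subjects who completed double-blind treatment. They are not premature double-blind stops, and leaving them out of PDISCTR follows the plan's definition. A subject stopped at Visit 7 before the last double-blind dose can still be logged as a premature double-blind stop.
- That stops at Visit 7 appear in no by-arm table. If an AE marked as permanent discontinuation caused the stop, it reaches TEAEPDSCPR. The gap is in the tabulated treatment-stop reason, mainly for non-AE reasons.
- That treatment failure at Week 8 and rebound go uncompared between arms. Week 8 pressures are compared by arm in the primary and control-rate analyses, and Week 8 to Week 10 changes in the extended repeated-measures model (SAP 10.8). A table of stop reasons would supplement these.

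The two Key tables also answer different questions, and with subject listings for both, a determined reader could work out the differences.

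**Conclusion.** The point holds in a limited form. Under the intended window, AEs that stop withdrawal placebo are mixed by dose arm into TEAEPDSCPR and TEAEPDPR and cannot be separated there, while PDISCTR counts double-blind stops only, so the two can disagree for the same arm. For double-blind completers, reasons for not starting or for stopping the placebo are listed and not tabulated, which leaves non-AE reasons without a by-arm display.

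Protocol 11.3.5 supports the AE part directly, since it promised the safety analyses separately for the withdrawal period. It supports the reasons table less directly, because it covers only subjects who took part in that period.

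The size is unknown. One subject is worth about 1.2 points in an arm's AE-discontinuation rate, assuming equal arms of about 82. The documents offer no basis for predicting how many there would be. The primary efficacy analysis is untouched; what is affected is a per-dose tolerability figure in a dose-selection trial, which makes an inexpensive correction worth making.

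**What to change.** 1. Split TEAEPDSCPR and TEAEPDPR, by arm, into AEs that stopped double-blind treatment (linked to Study Drug Log period DB TREATMENT, as SAP 5.3.3 already does for stops) and AEs that stopped withdrawal placebo. Display both parts, so that possible carry-over or rebound events are kept.
2. Add one by-arm Safety Set table of reasons, with two groups: completed double-blind treatment and did not enter withdrawal; entered withdrawal and stopped early.
3. Correct the cross-references in SAP 5.6.1.1 from 11.2 and 11.4 to 11.5 and 11.6, and likewise where the same pair is used for deaths, SAEs, ECG and laboratory abnormalities. State in SAP 4.1.3 what becomes of the withdrawal-period safety analyses in Protocol 11.3.5.

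The cost is SAP wording, one extra table and a link from AE records to the Study Drug Log. The link is the main work: the documents do not show that the AE form records which period's drug was stopped, so it may have to be derived from Study Drug Log dates and reasons.

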5.3.4 Study treatment adjustments or interruptions

Study treatment interruptions in the double-blind period are recorded in the **Study drug Log** when 'Study Period' is 'DB TREATMENT'. A subject is considered to have had a study treatment interruption if the reason for treatment end is either 'Temporarily interrupted due to an AE' or 'Temporarily interrupted not due to an AE'.

5.4 Study discontinuation

Subjects who completed the study as per protocol are those with the question "Did the subject complete the study?" answered "Yes" in the **End-of-Study** eCRF.

On the other hand, a subject is considered to have prematurely discontinued the study if the answer to the question 'Did the subject complete the study?' in the **End-of-Study** eCRF is 'No'. The reason for study stop is derived from the same form. Reasons for study withdrawal are: Death, Lost to follow up, Subject decision, Physician decision, Sponsor decision.

5.5 Efficacy variables

All efficacy data are collected electronically and are transferred to Actelion by [REDACTED].

OBPM, SiDBP and SiSBP (mmHg) are measured at the study site by the BpTRU[®] device using six measurements per subject / visit. These measurements and their average (excluding the first measurement) are uploaded into the [REDACTED] database. The data

transfer from [REDACTED] to Actelion includes the separate measurements as well as the average which will be used as the subject's SiDBP or SiSBP value for that visit. The average will not be re-calculated by the sponsor. The sponsor will perform spot checks to confirm that the average was been correctly calculated [REDACTED]

ABPM is performed over a 24-h period with the ABPM device set to record DBP and SBP at a pre-defined inflation sequence over the 24-h period including three measurements per hour during the day and two per hour during the night. ABPM data are electronically transferred to [REDACTED] and subsequently to Actelion. The [REDACTED] supplements each ABPM reading with an indicator of whether the reading satisfied the quality control criteria agreed between [REDACTED] and Actelion [REDACTED]

1. Start time of ABPM is between 06:00 and 11:00
2. Duration of ABPM is at least 24 hours
3. Percentage of valid readings in the period of duration is at least 75%
4. Number of required hours (i.e., hours with at least one reading) is at least 22
5. Number of exception hours (i.e., hours without a reading) is at most 2
6. No two consecutive exception hours

In addition, there is an indicator (Y/N) for the overall quality of the ABPM reading. This is only set to Y if all six criteria are met.

It should be noted that when an ABPM reading does not satisfy all 6 criteria, this does not necessarily mean that this reading should be excluded from the analysis as the ABPM analysis primarily focuses on the 24 hour means [REDACTED]. For the analysis of 24 hour means, criteria 3 and 6 are considered to be the most relevant ones by Actelion.

For this reason, the ABPM analyses will be based on the subset of subjects from the PPS with baseline and Week 8 ABPM readings satisfying quality criteria 3 and 6 (i.e., ABPM readings having less than 75% valid readings and/or two consecutive exception hours will be excluded). As this subset is likely to be comprised of < 50% of subjects, formal dose-response analyses for the ABPM endpoints will be carried out as needed.

All assessments (including the unscheduled ones) are considered and re-assigned to the most appropriate visit according to the time windows described in Section 11; reference to visits are to be intended as references to re-mapped visit, i.e., time window visits.

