3.2 Secondary objectives

- Evaluate the dose-response of ACT-132577 on:
 - Systolic blood pressure (SBP)
 - Control and response rate of blood pressure (BP)
 - 24-h ABPM.
- Evaluate the safety and tolerability of a once a day (o.d.) oral regimen of 4 doses of ACT-132577.

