 - Group level: for each hour after drug intake (0, 1, ..., 24) and the treatment group the difference in mean ABPM-DBP between Week 8 (Visit 7 Part 1) and baseline (Visit 4 Part 1) will be obtained.
 - Group level: the trough to peak ratio will be calculated as the average of the (five) differences at hours 20–24 (expected trough) divided by the average of the (five) differences at hours 2–6 (expected peak at 4 hours \pm 2 hours) [See Appendix C for illustration.]

Baseline is defined as described in Section 5 and Week 8 is the time window of Visit 7 [Section 11.1].

In the evaluation of changes from baseline and control/response status, only subjects with both the baseline and the time point assessments available will be included.

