10.7 Analysis of the secondary efficacy variables

Secondary efficacy variables will be analyzed for the PPS at $\alpha = 0.05$ (two-sided) using 95% CIs. Additionally, change from baseline to Week 8 in mean trough SiSBP will be analyzed for the FAS. No correction for multiple testing will be applied for these analyses.

Change from baseline to Week 8 of DB treatment period (Period II) in mean trough SiSBP will be analyzed similarly to the primary endpoint (SiDBP), i.e., MCP-Mod will be applied, supplemented by the ANCOVA and the repeated measurements models described above. The correlation between the changes from baseline in SiDBP and SiSBP will be displayed in a scatter plot for each post-baseline time point.

Control (< 90 mmHg and < 85 mmHg, separately) and response (Y/N) at Week 8 of DB treatment period (Period II) based on trough SiDBP will be analyzed using a logistic regression model with a factor for treatment group and a covariate for baseline mean trough SiDBP. Control and response status at Week 8 of Period II based on trough SiSBP will be analyzed similarly.

Change from baseline to Week 8 of DB treatment period (Period II) in 24-hour mean DBP based on ABPM will be analyzed using an ANCOVA with a factor for treatment group and a covariate for baseline 24-hour mean DBP. Change from baseline to Week 8 of DB treatment period (Period II) in 24-hour mean SBP based on ABPM will be analyzed similarly.

The baseline and Week 8 average ABPM-DBP curves over time (by hour) will be plotted by treatment group [averaging as described in Section 5.5.2]. Additionally, the Week 8 minus baseline difference will be plotted vs time. Trough to peak ratios for DBP will be calculated by treatment group as described in Section 5.5.2.

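### The ABPM analyses drop any valid Week 8 recording that lacks a valid baseline recording, and the formal dose-response analysis for the 24-hour ABPM objective is left to discretion

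*SAP*

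**What the plan says.** SAP 5.5 (and 4.1.2) limits all ABPM analyses to the "subset of subjects from the PPS with baseline and Week 8 ABPM readings satisfying quality criteria 3 and 6". Criterion 3 asks for at least 75% valid readings; criterion 6 rules out two consecutive hours without a reading. SAP 5.5.2 repeats the pairing rule for changes from baseline: "only subjects with both the baseline and the time point assessments available will be included".

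On the consequence, SAP 5.5 says "this subset is likely to be comprised of < 50% of subjects" and that "formal dose-response analyses for the ABPM endpoints will be carried out as needed". It does not say what would make the analysis needed, who decides, or when.

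The objective in SAP 3.2 reads "Evaluate the dose-response of ACT-132577 on" and lists 24-hour ABPM as one of three items; Protocol 2.2 agrees.

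What is fixed for ABPM is in SAP 10.7: change to Week 8 in "24-hour mean DBP based on ABPM will be analyzed using an ANCOVA with a factor for treatment group", with the baseline value as covariate. The 24-hour SBP is handled in the same way, and SAP 10.8 does this for daytime and night-time means. SAP Table 4 assigns every ABPM row to the paired PPS subset, with no MCP-Mod, mixed-model or FAS row. Office SiSBP has all three. SAP 13.7 lists no ABPM MCP-Mod output.

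**The concern.** Two separate things are at issue.

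The first is precision. The baseline ABPM is recorded on run-in placebo, and the device comes off before the first double-blind dose (Protocol 8.1.4.1 and 8.2.1). Treatment cannot cause a failed baseline recording, and the expected baseline mean is common to all arms. A Week 8 recording without a baseline partner therefore still informs the comparison between arms. An ANCOVA on change cannot use it; a likelihood model can.

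The second is pre-specification. A discretionary dose-response test for a named objective can be decided on after results are seen. A small subset widens the intervals, but that is no reason to leave open whether the test is run.

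**Working it through.** **Inputs in the documents.** Paired share under 50%, denominator not stated (SAP 5.5). Planned PPS of 70 per group (Protocol 11.5.1). 490 randomized after re-estimation (SAP 4.2), so about 490/6 × 0.8 = 65 per group in the PPS. Office SiDBP SDs of 7–9 mmHg and maximum differences of 4–5 mmHg.

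**Inputs not in the documents.** ABPM validity rate at each visit, baseline–Week 8 correlation, ABPM SD and ABPM effect. The under-50% figure therefore cannot be reproduced, and the values below are assumptions.

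**The plan's power figures.** The power program in the re-estimation SAP (15.2), recoded, reproduces Protocol Table 4: 19 of 21 cells exactly and two within 1 per group (for example, 63 per group for 90% power at SD 9).

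**What a half-sized set means for a formal test.** 0.49 × 70 ≈ 34 per group. Borrowing the office SiDBP effects as a stand-in for ABPM, average power over the four curves changes as follows:

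| SD (mmHg) | 70 per group | 34 per group |
|---|---|---|
| 7 | 99.1% | 86.8% |
| 8 | 96.9% | 77.3% |
| 9 | 92.9% | 67.6% |

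Confidence intervals widen by √(1/0.49) ≈ 1.43. This is the effect of the whole shortfall, not only of the part that a different model can recover.

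**The recoverable part.** Let p_both be the share of the PPS with both recordings valid, p_8 the share with a valid Week 8 recording, and ρ the correlation. With a common baseline mean and unit variance, a paired subject contributes 1/(1 − ρ²) to the information on the Week 8 arm means. A Week 8-only subject contributes 1. A baseline-only subject adds nothing to arm differences. Hence

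relative gain = (p_8 − p_both)(1 − ρ²) / p_both.

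With p_both = 0.50:

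| Validity pattern | p_8 | (p_8 − 0.50)/0.50 | ρ = 0.5 (× 0.75) | ρ = 0.6 (× 0.64) | ρ = 0.7 (× 0.51) |
|---|---|---|---|---|---|
| Failures independent, equal rates | √0.50 = 0.707 | 0.414 | 31% | 27% | 21% |
| Failures partly clustered | 0.60 | 0.20 | 15% | 13% | 10% |
| Failures coincide fully | 0.50 | 0 | 0% | 0% | 0% |

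In the independent case, of the 50 points lost from the PPS, 100 − 71 = 29 are failed Week 8 recordings that no model recovers, and 71 − 50 = 21 are failed baselines with a valid Week 8.

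**Check.** Generalized least squares for five arms of 70, with 70% valid at each visit and 49% paired, gives variance ratios of 1.32, 1.22 and 1.15 for ρ = 0.5, 0.7 and 0.8. The formula agrees: 0.21 × 0.75/0.49 = 0.32 at ρ = 0.5. In that case the effective size rises from 34 to between 34 × 1.15 ≈ 39 and 34 × 1.32 ≈ 45 per group, and power at SD 8 from 77% to about 82–87%.

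**Sensitivity to the assumptions.** If the under-50% refers to randomized subjects with 80% in the PPS, the paired share of the PPS is 0.50/0.80 = 0.625. Independent failures then give p_8 = 0.791 and a gain of 0.265 × (0.51 to 0.75), about 14–20%. If baseline recordings fail more often (60% valid at baseline, 80% at Week 8, 48% paired), the gain at ρ = 0.5 is (0.32/0.48) × 0.75 = 50%. The 10–31% range is therefore illustrative, not a bound.

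**The case against.** The endpoint is a change from baseline, so a simple change score needs both recordings. ANCOVA on complete pairs is standard, and it is what Protocol 11.3.3 planned for ABPM, so nothing promised for the 24-hour means was withdrawn. SAP 10.1 calls everything outside the main analysis exploratory. The SAP already limits the loss by requiring two of the six quality criteria. The dose-group ANCOVA gives four dose-versus-placebo estimates, its 24-hour DBP output is marked as key in SAP 13.7, and hourly curves by dose group are also planned. The gain is unknown and may be zero. Paired ANCOVA also tolerates recording failure that depends on the unrecorded baseline, whereas a model with baseline as an outcome assumes missing at random for baseline too.

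All of this stands, and it limits the size and weight of the point. It does not show a reason to discard a valid Week 8 recording, and it does not supply the missing trigger for the formal analysis. On the assumption, SAP 9.1 already accepts missing at random for its mixed models, and baseline failure precedes randomization, which should limit any effect on arm differences.

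**Conclusion.** The point holds as a recommended change to a secondary, exploratory analysis. The pairing rule discards any valid Week 8 recording without a valid baseline, and the formal ABPM dose-response analysis has no stated trigger. Under the assumptions of 50% paired, 60–71% valid at Week 8 and correlation 0.5–0.7, using all valid recordings adds about 10–31% information. The gain is zero if failures coincide fully within subjects. The case for fixing the dose-response analysis in advance does not depend on that gain.

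Three stronger readings are not supported:

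- A reader might infer that the pairing rule itself removes more than half of subjects. The under-50% figure also counts failed Week 8 recordings, which are lost under any method, and it is an expectation rather than a count.
- A reader might infer that the ABPM objective could end with no result by dose. The ANCOVA by dose group is fixed in SAP 10.7, 10.8 and Table 4; only the formal dose-response analysis is optional.
- A reader might take the power figures above as ABPM power. They borrow office SiDBP effects and SDs, because the documents give none for ABPM.

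**What to change.** In SAP 5.5, 10.7, 10.8 and Table 4:

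1. Analyze 24-hour, daytime and night-time DBP and SBP with a constrained longitudinal model: baseline and Week 8 as two outcomes, one baseline mean common to all arms, treatment means at Week 8, and an unstructured 2 × 2 covariance. Include all PPS subjects with at least one recording that meets criteria 3 and 6. Baseline must move to the outcome side; as a covariate, as in the SAP 9.3 code, it would still drop these subjects.
2. Pass the Week 8 LSMeans and their covariance for 24-hour DBP and SBP to the general MCP-Mod of SAP 9.3 as a fixed exploratory analysis, replacing the as-needed wording. SAP 9.3 is now written for office BP endpoints, so extend its scope and state the target difference to be used for ABPM.
3. Keep the complete-pair ANCOVA as a sensitivity analysis.
4. Update SAP 13.7 and 13.8. SAP 13.7 currently lists the 24-hour SBP ANCOVA only for lisinopril versus placebo, although SAP 10.7 plans it by treatment group.

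No new data are needed. The cost is SAP wording, six model fits, two MCP-Mod runs and their outputs, and the wider missing-at-random assumption. The trough-to-peak ratio would still rest on the paired subset, so state that its subjects differ from those behind the 24-hour means. Tabulating recording validity by visit and arm would show how much was recovered.
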